4.1 General Study Design and Plan

The goal of the first experiment was to select the lowest dose of VCN to produce high (90%) receptor occupancy. $\alpha 4\beta 2^*$ nAChR receptor occupancy is defined as the difference between [¹⁸F]Flubatine binding before and VCN discontinuation, i.e., 10 days after initiation of VCN administration (Day 10) and 5 days after VCN discontinuation (Day 15).

The goal is to have 3/3 subjects achieve >90% receptor occupancy. The dose schedule will be increment, as shown in the figure above, until there is no additional reduction in [18F]Flubatine binding, i.e., remaining binding is non-specific binding, and the penultimate maximum dose will define the dose to be used in the future crossover study.

The second experiment replicates the first experiment in a healthy volunteer population, matched for age. This experiment occurred after the results of the first experiment were known. Thus, only 3 dose groups were assess: 0.25 mg QD, 0.25 mg BID and 0.5 mg BID.

Participants received their first dose of varenicline on Day 1, followed by dose escalations on days 2 and 3 (as needed). On Day 10, they discontinued varenicline and received their first flubatine PET scan. Five days after discontinuation of varenicline (Day 15), they received their second flubatine PET scan.

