participants), to establish the required oral dose for **SA2** and **SA3** experiments. The results of the initial (0.25 mg/day maximum dose) study will be used to select the next dose point. If there is a substantial effect on [F]flubatine binding (>50% reduction), we will use the 0.25 mg bid maximum dose schedule for the next experiment. If the effect on [F]flubatine binding is <50% reduction, we will use 0.5 mg bid maximum dose schedule for the next experiment. Selection of the subsequent dose schedule will be based on the results of the 0.5 mg bid maximum dose experiment. We will increment dose schedules until there is no additional reduction in [F]flubatine binding, i.e., remaining binding is non-specific binding, and the penultimate maximum dose defines our **SA2-SA3** study dose. Based on the work of Lotfipour et al., who found that a single oral 0.5 mg VCN dose produced ~100% receptor occupancy (70), we don't anticipate using the highest (1 mg po bid) dose schedule). We will measure plasma VCN levels at the time of the initial scan (Pharmacokinetics Core, U- M College of Pharmacy; see attached letter from [name], Core Director). These measurements are not for formal PK studies as VCN PK is well established, but rather to confirm study drug compliance. We aim to establish the lowest dose producing high (~100%) receptor occupancy and if we achieve this goal after studying 2 dose schedules (6 participants total), we will stop and proceed to **SA2** experiments.

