Following completion of the PD subject study experiment 1, we will perform a limited experiment to assess  $\alpha 4\beta 2^*$  nAChR occupancy in age-matched controls. Controls will receive VCN (no placebo) for 10 days. We will select a subset of the doses used for the PD subjects in experiment 1 to assess receptor occupancy in normal controls. Assuming we don't detect very high (>90%) occupancy with our initial dose (0.25 mg/day), we will expose controls to one of three different dosages of varenicline to construct a dose-occupancy relationship for comparison with the results in PD subjects. Based on the results of experiment 1, experiment 2 will include the following dosages

with a goal of 3 patients per cohort: .25mg QD, .25mg BID and .5mg BID. All procedures will be identical to experiment 1. Control subjects will be drawn from the normal control pool characterized concurrently in the Clinical Core of the Udall project, much as the PD subjects are drawn from the pool of PD subjects. Control subjects will also be recruited from the UM Health Research website if needed. We anticipate studying 9 subjects, 3 at each dosage point. To adjust for potential dropouts, we will budget 12 control subjects.

**Potential Problems and Alternatives:** The results of Loftipour et al. suggest that low doses will produce high  $\alpha 4\beta 2^*$  nAChR occupancy (70). Commercially available VCN pills are small and division beyond bisection is likely to be inaccurate. 0.25 mg/day is the lowest feasible dose and if we find this dose produces high per cent receptor occupancy, no further testing will be necessary. VCN tolerability may be a problem as this agent has not been tried specifically in PD subjects previously. To avoid any problems, we are starting with low doses and using an incrementing schedule. Nausea was infrequent in a recent trial in AD which used significantly higher doses (89). If tolerability is an issue, then we will alter the incrementing schedule to more gradually “ramp” up to the desired dose.

**Specific Aim 2: To assess the effects of pharmacologic  $\alpha 4\beta 2^*$  nAChR activation on laboratory measures of gait function and postural control in PD subjects with cholinergic deficits.**

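### The SAP describes the crossover dose both as the lowest schedule above 90% occupancy and as the penultimate schedule before a plateau. These can differ two-fold, and the 90% criterion rests on a ratio that understates occupancy.

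*SAP*

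**What the plan says.** SAP 4.1 contains three statements about the dose:

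- The aim: "The goal of the first experiment was to select the lowest dose of VCN to produce high (90%) receptor occupancy".
- A per-person form of it: "The goal is to have 3/3 subjects achieve >90% receptor occupancy".
- A plateau rule: escalate until binding falls no further, at which point "the penultimate maximum dose will define the dose to be used in the future crossover study".

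The protocol carries both ideas. Overall Rationale and Organization takes the lowest dose with high occupancy into Specific Aim 2, and the Specific Aim 1 rationale puts high at above 90%. The Specific Aim 1 procedures then say "We will increment dose schedules until there is no additional reduction in [ 18 F]flubatine binding, i.e., remaining binding is non-specific binding", and let the penultimate schedule define the study dose.

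Two early stops put occupancy first. For 0.25 mg/day, "if we find this dose produces high per cent receptor occupancy, no further testing will be necessary". After two schedules, escalation ends if the goal is met, and there the goal is glossed as about 100%, not 90%.

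Occupancy is defined in SAP 3.2.1 and 4.5 as (Day 10 - Day 15)/Day 15 x 100%. The SAP does not name the binding measure. The protocol's primary measure (Standard Methods, Flubatine PET Imaging) is late tissue activity over plasma tracer, which approximates the total distribution volume, V_T.

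**The concern.** A threshold and a plateau are different targets. On a dose list that doubles at every step, a schedule can pass 90% while the next one still lowers binding. The plan then points to two doses, and SAP 8 offers only descriptive statistics by cohort and dose group. The visible text names neither the dose carried forward nor the criterion that chose it.

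Two claims in the protocol's Specific Aim 2 (Potential Problems and Alternatives) depend on the dose. It relies on the lowest high-occupancy dose as protection against poor tolerability and dropout. It would also read a null crossover as pointing the field to other cholinergic receptors. The first needs a dose no higher than the lowest schedule above 90%. The second needs evidence that the receptors were in fact highly occupied, which a V_T ratio may be unable to give.

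**Working it through.** **Inputs.** Maximum daily doses are 0.25, 0.5, 1 and 2 mg (0.25 mg once daily, then 0.25, 0.5 and 1 mg bid; Protocol, Specific Aim 1), so each step is x2. The protocol anticipates 3 dose points x 3 people = 9, and 2 x 3 = 6 at the two-schedule stop; both figures reproduce. Neither document gives a test-retest SD for occupancy.

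**How far experiment 1 went.** For controls the protocol says "We will select a subset of the doses used for the PD subjects in experiment 1", and both documents list 0.25 mg once daily, 0.25 mg bid and 0.5 mg bid. The SAP adds of the control experiment: "This experiment occurred after the results of the first experiment were known". This implies at least three schedules in the patients. It is an inference, since neither document lists the doses the patients received.

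**The rules on one profile.** Suppose means of 86, 92, 96 and 96%. Schedule 1 is not above 90%. Schedule 2 is above 90% but not about 100%, so as written escalation continues. Schedule 4 adds nothing, so the penultimate schedule is 0.5 mg bid (1 mg/day). The lowest schedule above 90% is 0.25 mg bid (0.5 mg/day). The ratio is 1/0.5 = 2. If the two-schedule stop means above 90%, both routes end at 0.25 mg bid.

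**Size without noise.** Assume one-site binding, occupancy = D/(D + ED50). If 0.25 mg bid is the lowest schedule above 90%, schedule 1 lies between 81.8 and 90.0%. The profiles run from 81.8/90.0/94.7/97.3 to 90.0/94.7/97.3/98.6. Schedule 2 is then 90.0 to 94.7%, short of even a 95% reading of about 100%. Occupancy still rises 2.6 to 4.7 points at the next step.

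**Size with noise.** Truth 86/92.5/96.1/98.0, cohorts of three, assumed per-person SD 2/4/6 points, and any numerical fall in binding continues escalation. If no plateau appears by 1 mg bid, 0.5 mg bid is counted as chosen.

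| Two-schedule stop | Plateau route above 0.25 mg bid | The two rules differ |
|---|---|---|
| mean at least 95% | 98/75/55% | 96/64/43% |
| mean above 90% | about 2/12/16% | 0/1/5% |

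Simply taking the first mean above 90% goes too high in 2/14/21%, so under the second reading the plateau route is no worse. Where 0.5 mg bid is the lowest schedule above 90%, the comparison turns mostly on how a list that ends without a plateau is scored, so I draw nothing from it.

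**The per-person form.** At a true 92.5%, the chance that all three exceed 90% is Phi(2.5/SD)^3 = 72/40/29% for SD 2/4/6. A schedule can meet the aim on its mean and miss this goal.

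**The occupancy ratio.** Let O be true occupancy, V_ND the non-displaceable volume and f = V_ND/(Day 15 V_T). Then Day 10 V_T = V_ND + (1 - O)(Day 15 V_T - V_ND), and

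(Day 15 - Day 10)/Day 15 = O(1 - f).

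- O = 100%, f = 20%: reads 80%.
- O = 100%, f = 10%: reads 90%, the most it can reach.
- O = 95%: reading 90% needs f no more than 1 - 0.90/0.95 = 5.3%.
- Truth 86/92.5/96.1/98.0 with f = 20%: reads 68.8/74.0/76.9/78.4. No schedule passes 90%.

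The documents give no f; 10% and 20% are illustrations. The plan does expect f above zero, since it describes the binding left at the plateau as non-specific. As printed, the SAP ratio also comes out negative when the drug lowers binding.

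**The case against.** The strongest reply is that the order is stated: the 90% sentences are worded as goals, and only the plateau sentence says which dose goes forward. That is a fair reading of SAP 4.1 alone. It does not settle the matter, because Overall Rationale and Organization and the Specific Aim 1 rationale give the same role to the lowest high-occupancy dose.

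The second reply is that high means above 90% almost everywhere in the documents, and the about-100% gloss sits only in the stopping sentence. The protocol even quotes the same cited result as about 95% in one place and about 100% in another. This stands, and it limits the point: under the above-90% reading the two-fold gap largely disappears.

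The third reply is that little hangs on it. One step too high from 0.25 mg bid is 1 mg/day, half the usual 2 mg/day. Enrolling 42 for 33 needed absorbs 9 dropouts (9/42 = 21%). The protocol also allows dose reduction for intolerance. This too stands, and keeps the severity down.

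A reader might infer more than the documents support:

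- That the wrong dose was chosen. The doses given and chosen in experiment 1 are not stated, and the SAP dose figure and Protocol Appendix 2 are not visible.
- That the plateau rule tends to select too low a dose. That result needs mostly a tolerance such as 3 or 5 points, which the documents do not give, and it ignores their definition of a plateau as only non-specific binding remaining.
- That a three-of-three goal contradicts groups of four. SAP 5 calls four the initial plan, and the protocol plans three per dose point.
- That the 6.9% thalamic coefficient of variation in Protocol Table 2 measures scan error. It is between-subject variation in three controls. The SDs above are therefore assumptions.

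**Conclusion.** The point holds in limited form. The crossover dose is described by two criteria that the protocol does not clearly rank. If the two-schedule stop means about 100%, they can differ two-fold, upwards, when 0.25 mg bid lands at 90 to 95%. If it means above 90%, they nearly always agree in that case. The percentages rest on one-site binding and assumed SDs; the factor of two rests only on the dose list. Divergence is possible, not demonstrated.

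The occupancy ratio is the firmer part, provided the SAP's binding values are the protocol's primary V_T measure. It understates occupancy by the factor (1 - f) and cannot reach 90% once V_ND exceeds 10% of Day 15 V_T. That can leave the threshold without an answer, and it weakens any claim that a null crossover was obtained at high occupancy. Severity lies between an optional and a recommended change.

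**What to change.** Do not add a selection rule or ranking now. Experiment 1 was already known when the SAP described it, and a rule written afterwards could contradict the dose actually chosen.

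1. In SAP 3.2.1, 4.5 and 8, compute thalamic occupancy as (Day 15 - Day 10)/(Day 15 - V_ND). Take V_ND from an occupancy plot: regress Day 15 minus Day 10 V_T on Day 15 V_T across regions, and read V_ND as the x-intercept. Check the result against the white-matter reference-tissue analysis already planned. Name the binding measure, and keep the uncorrected ratio, with its sign reversed, as a sensitivity result.
2. In SAP 8, add one table of patient schedules in the order tested: individual and mean occupancy, number above 90%, the dose each of the three statements in SAP 4.1 gives, the dose carried forward, and the criterion that chose it.
3. If the criteria agree, nothing more is needed. If not, justify the dose in the Specific Aim 2 procedures, and qualify the tolerability argument and the reading of a null result.

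The cost is a few sentences, one table and a reanalysis of existing scans; no past decision changes. The downside is that the occupancy plot assumes equal occupancy and V_ND across regions. The three planned regions (thalamus, striatum, cerebellum) make a thin regression, and adding lower-binding regions brings in the variability the protocol wanted to avoid.

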4.2 Inclusion-Exclusion Criteria for Experiment 1 (PD patients with cholinergic deficits)

4.2.1 Inclusion Criteria

1. PD diagnosis will be based on the United Kingdom Parkinson's Disease Society Brain Bank Research Center (UKPDSBRC) clinical diagnostic criteria. We will enrich the cohort by recruiting subjects at modified Hoehn and Yahr stages 2 or higher, duration of motor disease 5 years or longer, age >65 years, or the PIGD phenotype. Duration of motor disease will be defined as the time between onset of motor symptoms and time of entry into the study. The PIGD phenotype is defined as described previously. PD subjects with defined cholinergic deficits will be recruited as described in Project II. PD subjects will have cortical cholinergic deficits based on 5th percentile cutoff of the normal controls as defined previously.
2. Stable dopaminergic replacement therapy for 3 months prior to enrollment and expected to maintain stable dopaminergic therapy for duration of study participation.

4.2.2 Exclusion Criteria

1. Other disorders which may resemble PD with or without dementia, such as vascular dementia, normal pressure hydrocephalus, progressive supranuclear palsy, multiple system atrophy, corticobasal ganglionic degeneration, or toxic causes of parkinsonism. Prototypical cases have distinctive clinical profiles, like vertical supranuclear gaze palsy, early and severe dysautonomia or appendicular apraxia, which may differentiate them from idiopathic PD. The use of the UKPDSBRC clinical diagnostic criteria for PD will mitigate the inclusion of subjects with atypical parkinsonism and all participants will undergo [¹¹C]DTBZ PET to confirm striatal dopaminergic denervation.
2. Subjects on neuroleptic, anticholinergic (trihexiphenidyl, benzotropine), or cholinesterase inhibitor drugs.
3. Current or previous (within last 6 months) use of any product or medication containing nicotinic agents, including use of tobacco products such as cigarettes, cigars, pipes, chewing tobacco, etc., e-cigarettes, OTC nicotine patches, chewing gum containing nicotine, or varenicline.
4. Evidence of a stroke or mass lesion on structural brain imaging (MRI).

5. Participants in whom magnetic resonance imaging (MRI) is contraindicated including, but not limited to, those with a pacemaker, presence of metallic fragments near the eyes or spinal cord, or cochlear implant.
6. Severe claustrophobia precluding MR or PET imaging
7. Subjects limited by participation in research procedures involving ionizing radiation.
8. Pregnancy (test within 48 hours of each PET session) or breastfeeding.
9. Significant risk of cardiovascular event.
10. Active, significant mood disorder.
11. History of seizures.
12. Active alcohol abuse.

4.3 Inclusion-Exclusion Criteria for Experiment 2 (Healthy Controls)

Normal healthy control individuals age 45 years and older without any history of neurological disease.

4.4 Randomization and Blinding

These experiments were not randomized nor was blinding employed.

4.5 Study Assessments

The primary outcome is $\alpha 4\beta 2^*$ nAChR receptor occupancy, defined as the difference between [¹⁸F]Flubatine binding before and VCN discontinuation, i.e., 10 days after initiation of VCN administration (Day 10) and 5 days after VCN discontinuation (Day 15). Specifically, receptor occupancy is defined as $[(\text{Day 10} - \text{Day 15}) / \text{Day 15}] \times 100\%$.

Adverse events were also collected throughout the 15-day study period.

5 Sample Size

The sample size (planned initially at four PD participants per dosing group) for the VCN- $\alpha 4\beta 2^*$ nAChR occupancy study was based on logistical considerations. The selection of 10 control participants was also based on logistical considerations.

6 General Analysis Considerations

6.1 Timing of Analyses

The final analysis was completed after all all PD and control participants completed their follow-up.

6.2 Analysis Populations

All consented participants who received at least one dose of study medication will be used in the analyses of demographic and baseline characteristics and safety. Only participants who were able to complete sufficient treatment and PET images were included in the analyses of VCN- $\alpha 4\beta 2^*$ nAChR occupancy.

6.3 Covariates and Subgroups

No covariates nor subgroups were incorporated into analyses.

6.4 Missing Data

No imputation methods will be used.

6.5 Interim Analyses and Data Monitoring

No formal interim analyses were planned nor carried out for this study. The study was overseen by a Data and Safety Monitoring Board (DSMB) that reviewed the subject disposition, study conduct and safety data approximately every 6 months.

7 Summary of Study Data

Descriptive summary statistics will be derived for all data at baseline, separately by cohort (i.e., PD and control participant groups) and overall.

For continuous variables, mean, standard deviation, median, interquartile range, minimum and maximum will be reported. For categorical variables, number and percentages will be reported (excluding missing values). Graphical methods will be heavily used in this pilot study to assess the pattern of response over time for key variables and to assess the relationships among variables.

7.1 Subject Disposition

The number of participants approached for study participation, the number consented and the number who did not consent (including reasons: screen failures, refusals) will be summarized in a CONSORT diagram. The number of participants who dropped out after initiation of study medication administration and the reasons for dropout will be summarized.

7.2 Protocol Deviations

Listings of protocol deviations will be provided by study cohort.

7.3 Demographic and Baseline Variables

Demographic variables include: age at consent (defined as a continuous variable, e.g., 52.6 years), sex, race and ethnicity.

Baseline is defined as pre-treatment measures. Baseline variables include:

- Age at diagnosis (years)
- MDS-UPDRS III total score
- GDS score
- MoCA score

7.4 Treatment Compliance

A listing of compliance with study medication (# of doses taken by day) will be provided by study cohort.

8 Efficacy Analyses

Descriptive statistics for receptor occupancy will be provided by study cohort and by dose group.

9 Safety Analyses

Safety endpoints will be analyzed in all randomized participants who received at least one dose of study medication. Safety data, including adverse events (AEs) and the Columbia-Suicide Severity Rating Scale (C-SSRS), will be summarized descriptively by study cohort and by dose group.

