To demonstrate that  $\alpha 4\beta 2^*$  nAChRs are appropriate therapeutic targets in PD, it is necessary to study key pharmacokinetic-pharmacodynamic features of  $\alpha 4\beta 2^*$  nAChR *in the context of the degenerating, hypocholinergic PD brain*, a pathologic environment in which they may exhibit unique features. This *personalized medicine* approach focuses our studies on the subgroup of hypocholinergic PD subjects identified by **Project II** and the **Clinical Resource Core**. We will assess  $\alpha 4\beta 2^*$  nAChR features using PET imaging with the  $\alpha 4\beta 2^*$  nAChR ligand [ $^{18}\text{F}$ ]flubatine, subacute administration of the  $\alpha 4\beta 2^*$  nAChR partial agonist varenicline (VCN), and laboratory measures of gait, balance, and attention. We will use [ $^{18}\text{F}$ ]flubatine PET to assess VCN occupancy of brain  $\alpha 4\beta 2^*$  nAChRs. Using this PET data to select an appropriate VCN dose, we will perform a pharmacodynamic study with subacute VCN administration to determine if  $\alpha 4\beta 2^*$  nAChR stimulation improves laboratory measures of gait function, postural control, and attentional function in hypocholinergic PD subjects.

**Specific Aim 1:** To use [ $^{18}\text{F}$ ]flubatine PET to assess VCN occupancy of brain  $\alpha 4\beta 2^*$  nAChRs after subacute VCN administration to the subgroup of PD subjects with cholinergic deficits in comparison with normal control subjects.

**Hypothesis 1a:** Low dose, subacute VCN administration produces high  $\alpha 4\beta 2^*$  nAChR occupancy in PD subjects with cholinergic deficits.

**Hypothesis 1b:** Low dose, subacute VCN administration produces equivalent  $\alpha 4\beta 2^*$  nAChR occupancy in PD subjects with cholinergic deficits and normal control subjects.

**Specific Aim 2:** To assess the effects of pharmacologic  $\alpha 4\beta 2^*$  nAChR activation on laboratory measures of gait function and postural control in PD subjects with cholinergic deficits.

**Hypothesis 2:** Pharmacologic  $\alpha 4\beta 2^*$  nAChR activation in PD subjects with cholinergic deficits will improve laboratory measures of gait function and postural control.

**Specific Aim 3:** To assess the effects of pharmacologic  $\alpha 4\beta 2^*$  nAChR activation on a measure of attentional function (SAT; sustained attention test) in PD subjects with cholinergic deficits.

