We will investigate the possibility that regulation of  $\alpha 4\beta 2^*$  nAChRs might be different in PD brain versus brains of normal individuals. We will investigate this possibility with a focused study of  $\alpha 4\beta 2^*$  nAChR receptor occupancy in a small group of normal subjects. Following the conclusion of receptor occupancy studies in hypocholinergic PD subjects, we will perform a more limited, parallel, dose-receptor occupancy study to determine if there are major differences in VCN receptor occupancy between PD and control subjects.

**Subject Selection:** PD subjects will be drawn from **Project II** subjects who have undergone  $[^{18}\text{F}]\text{FEOBV}$  imaging to identify cholinergic deficits.

We will study subjects with cortical innervation deficits below the 5th percentile cutoff of controls as defined previously (17). General inclusion and exclusion criteria are specified in the **Clinical Resource Core** and **Project II**. Current or previous (within last 6 months) use of any product or medication containing nicotinic agents, including use of tobacco products such as cigarettes, cigars, pipes, chewing tobacco, etc., e-cigarettes, OTC nicotine patches, chewing gum containing nicotine, or varenicline is an exclusion. While most data does not indicate that VCN causes suicidality or cardiovascular problems (73 - 81), we will exclude subjects with depression, active cardiovascular disease, history of seizures, or alcohol use disorders. (see **Human Subject Protection**).

[figure not shown]
The **Clinical Resource Core** and **Project II** project initial enrollment of 95 PD subjects with longitudinal follow-up of 75 PD subjects. Based on prior results, we project that 30% (32) of the initially enrolled subjects will be hypocholinergic. Based on preliminary data (**Project II**), 25% (20) of the longitudinally followed PD subjects will convert from normo- to hypocholinergic during the project period. This gives a total of 52 eligible subjects (Table 1). Our long-standing experience is that a significant fraction of subjects participate in multiple experiments, so we anticipate little difficulty in recruiting the projected 55 PD subject-equivalents required. In our recently concluded Program Project Grant (NS15655), we studied 151 PD subjects. All underwent at least 2 PET studies with 112

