undergoing 3 or more scans (69 - 3 studies; 43 - 4 studies). We are basing our estimates on a stringent 5th percentile cut-off relative to our normal control database. We will carefully monitor subject recruitment to enroll the target number of hypocholinergic PD subjects. If needed, **Core B** will preferentially recruit an enriched sample of PD subjects with longer duration disease and/or mild cognitive changes, subjects more likely to exhibit cholinergic deficits. **Core B** will be aided in recruitment by the **Core D** (Education and Outreach Core). **Appendix 1** contains a detailed schedule of study activities.

**IND Exemption:** We obtained an IND exemption from the FDA.

**Specific Aim 1:** To use [F]flubatine PET to assess VCN occupancy of brain  $\alpha 4\beta 2^*$  nAChRs after subacute VCN administration to the subgroup of PD subjects with cholinergic deficits.

**Rationale and Predictions:** We will use [F]flubatine PET to select an appropriate VCN dose for **SA2** and **SA3** studies. Application of [F]flubatine PET will allow selection of the lowest dose producing high (>90%) receptor occupancy. Measuring VCN displacement of [F]flubatine obviates the need for clinical dose escalation studies in hypocholinergic PD subjects.  $\alpha 4\beta 2^*$  nAChRs are complex heteromeric proteins with highly regulated expression and function. These studies are essential, as the PD brain is a very different environment from a normal brain. We predict that these studies will identify a VCN dose at the lower end of the clinically used range producing high (>90%)  $\alpha 4\beta 2^*$  nAChR occupancy. A recent acute VCN dose study in acutely abstinent smokers (upregulated  $\alpha 4\beta 2^*$  nAChRs) with [F]FA-85380 reported that a single 0.5 mg

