3.1 Study Objectives

Primary Objective

- To use [¹⁸F]flubatine PET to assess varenicline (VCN) occupancy of brain $\alpha 4\beta 2^*$ nAChRs after subacute VCN administration to the subgroup of PD subjects with cholinergic deficits in comparison with normal control subjects.

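### Hypothesis 1b predicts equivalent occupancy in PD and controls, but SAP section 8 plans only summaries by cohort and dose, which cannot support an equivalence conclusion

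*SAP*

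**What the plan says.** **The hypothesis.** Under Specific Aim 1, Protocol Hypothesis 1b begins "Low dose, subacute VCN administration produces equivalent" and goes on to receptor occupancy in PD subjects with cholinergic deficits and normal controls. The SAP does not repeat the word equivalent. Its only stated objective (section 3.1) is to assess occupancy in PD "in comparison with normal control subjects".

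**The purpose of the experiments.** The Specific Aim 1 rationale says that PET "will allow selection of the lowest dose producing high (>90%) receptor occupancy", and SAP section 4.1 adds the working criterion: "The goal is to have 3/3 subjects achieve >90% receptor occupancy". The Protocol's Overall Rationale describes the control study as limited, and intended "to determine if there are major differences in VCN receptor occupancy between PD and control subjects". The control doses overlap with the PD doses by design: "We will select a subset of the doses used for the PD subjects in experiment 1".

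**The analysis.** The whole of SAP section 8 reads: "Descriptive statistics for receptor occupancy will be provided by study cohort and by dose group". SAP section 7 lists mean, SD, median, interquartile range and extremes, in a passage written for baseline data, and says graphs will be used heavily. SAP section 6.3 uses no covariates or subgroups.

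**Sizes and timing.** The Protocol expects three PD participants and three controls at each of three doses, with 12 controls budgeted. SAP section 5 gives four PD participants per dose group as first planned, and 10 controls, both on logistical grounds. On the control experiment, SAP section 4.1 states: "This experiment occurred after the results of the first experiment were known". SAP section 6.1 describes the final analysis as completed.

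**The concern.** Equivalence is a claim that a difference is smaller than some stated amount. It needs an estimate of the difference, an interval around it and a margin to hold it against. The plan has a hypothesis of equivalence and none of these three. Two sets of summary statistics side by side invite the reader to compare means by eye, and in cells of three or four similar means are compatible with a sizeable true difference.

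At stake is the answer to the question that the control experiment was added to address: whether varenicline occupies these receptors differently in the hypocholinergic PD brain. Without a stated rule, similar cohort means could be reported as Hypothesis 1b confirmed when the data show only that no large difference was seen.

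**Working it through.** **1. Is a between-cohort analysis planned anywhere?** The places where it could be:

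| Place | What it provides | Difference, interval or margin for PD v control? |
|---|---|---|
| SAP 8 | Descriptive statistics by cohort and dose | No |
| SAP 7 | Summary statistics for baseline data; graphs | No |
| SAP 6.3 | No covariates or subgroups | No |
| Protocol, Specific Aim 1, control experiment | A dose-occupancy relationship to set beside the PD results | No method named |
| Protocol, Analysis Method (under Specific Aim 2) | Exploratory graphs for all aims; mixed models with tests that compare treatments | No; the tests compare varenicline with placebo in the crossover |

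A non-significant difference test would not establish equivalence in any case.

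**2. Is there a figure to reproduce?** No. The occupancy study states no power, alpha, SD or margin. The power statement under Specific Aim 2 concerns gait speed and sway jerk in the crossover. Protocol Table 2 gives the between-subject spread of tracer binding in three controls, which is not the SD of occupancy.

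**3. How precise is a comparison at one dose?** For n1 PD participants and n2 controls with a common SD:

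half-width of the 90% interval = t(0.95, n1 + n2 − 2) × SD × √(1/n1 + 1/n2)

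- 3 v 3 (Protocol sizes): t(4) = 2.132; √(1/3 + 1/3) = 0.816; product 1.74 × SD.
- 4 v 3 (SAP PD size, three controls): t(5) = 2.015; √(1/4 + 1/3) = 0.764; product 1.54 × SD.

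The SAP does not say how the 10 controls divide over three doses. If they divide 3/3/4, one dose could have a 4 v 4 cell: t(6) = 1.943; √(1/4 + 1/4) = 0.707; product 1.37 × SD. Exclusions under SAP section 6.2 could make any cell smaller.

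With the SD assumed, in percentage points of occupancy:

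| Assumed SD | 3 v 3 half-width | 4 v 3 half-width |
|---|---|---|
| 2 | 1.741 × 2 = 3.5 | 1.539 × 2 = 3.1 |
| 5 | 1.741 × 5 = 8.7 | 1.539 × 5 = 7.7 |
| 10 | 1.741 × 10 = 17.4 | 1.539 × 10 = 15.4 |

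These widths apply even if the two observed means are identical.

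**4. What would an equivalence rule deliver?** The documents give no margin, so ±10 points is assumed purely for illustration. Draw the observed difference from a normal distribution with mean 0 and the standard error above, draw the estimated SD from the matching chi-squared distribution, and count how often the whole 90% interval falls within ±10 (400,000 draws):

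| Assumed SD | 3 v 3 | 4 v 3 |
|---|---|---|
| 2 | 99.9% | >99.9% |
| 5 | 38% | 49% |
| 10 | 3% | 3% |

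If three independent 3 v 3 cells must all pass, cube the 3 v 3 column: 0.999³ = 0.997, 0.38³ = 0.055 and 0.03³ = 0.00003. The answer runs from near certainty to almost never, depending on an SD that the documents do not supply.

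**The case against.** The strongest reply is that the plan does what its own objective asks. The SAP speaks of comparison, not equivalence, and the Protocol says that the control study looks for major differences in a limited group. Summaries by cohort and dose, with graphs, serve that purpose. Hypothesis 1b is a prediction in the narrative of a pilot, and no passage says that similar means will be reported as equivalence. A reader given means, SDs and cell sizes can also work out the intervals.

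Most of this stands, and it limits the point. A reader might infer three stronger things that the documents do not support:

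- **That dose selection is compromised.** It is not. The dose is chosen from PD data, and the controls were studied afterwards.
- **That the study needs more participants or a powered test.** Its sizes are openly logistical, and it claims no power for this comparison.
- **That equivalence is out of reach at these sizes.** With an SD near 2 points it would be within reach of a 10-point margin. What is missing is the margin and the interval.

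The reply does not remove the mismatch. A stated hypothesis of equivalence is attached to an analysis that cannot test it. If only description is meant, the hypothesis should say so.

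**Conclusion.** The point holds as a mismatch between Protocol Hypothesis 1b and SAP section 8. The planned summaries suit dose selection and a search for major differences, but they cannot carry an equivalence conclusion. That rests on the text alone and needs no assumed figure.

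The size of the uncertainty is firm only in SD units: about 1.74 SD either side at one dose for 3 v 3, and 1.54 SD for 4 v 3. These multiples assume normality and equal SDs in the two cohorts. In percentage points everything depends on the assumed SD, and the pass rates depend also on the assumed 10-point margin, so neither fixes a magnitude for this trial. Priority is low: what changes is the wording of one conclusion.

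**What to change.** 1. In SAP section 8, for each dose given to both cohorts, report the PD-minus-control difference in thalamic occupancy with a 90% confidence interval and the cell sizes. Note that t intervals in cells of three or four rely on normality and equal SDs, both doubtful for a percentage near its ceiling.
2. Restate Hypothesis 1b as a descriptive comparison, in line with the Protocol's aim of looking for major differences, and state that similar means will not be read as equivalence.
3. If the sponsor still wishes to claim equivalence, require the 90% interval at every shared dose to lie within a margin that the sponsor justifies. A pass at one dose should not suffice: it could be picked after the fact, and near saturation the cohorts may look alike whatever happens at lower doses. Label the margin post hoc, because the controls followed the PD results and the final analysis is described as completed.

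The cost is one sentence on the hypothesis and a few lines in SAP section 8, using data already collected. The downside is that the intervals will be wide, and with an SD of about 5 points or more the rule in item 3 would seldom be met at a 10-point margin.
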